## GLOSSARY OF ABBREVIATIONS

6MWT	6-Minute Walk Test
AE	Adverse event
APACHE II	Acute physiology and chronic health evaluation II
ICU	Intensive care unit
IMS	ICU Mobility Scale
RASS	Richmond Agitation-Sedation Scale

RCT	Randomised controlled trial
SAE	Serious adverse event
SF-36 v2	36-item Short Form Health Survey Version 2
SOFA	Sequential Organ Failure Assessment
RAND SF-36 v1	RAND 36-Item Health Survey 1.0 Questionnaire
WHODAS 2.0	World Health Organisation's Disability Assessment Schedule 2.0

## KEYWORDS

Early Ambulation; Critical Care  
Intensive Care; Patient Safety  
Vasoactive drugs

## STUDY SUMMARY

**TITLE** Investigating the safety of mobilising intensive care unit patients receiving vasoactive drugs: An exploratory observational study

**DESIGN** Exploratory observational study

**AIMS** 1. To describe current practice in one healthcare organisation of mobilising ICU patients receiving vasoactive drugs.  
2. To describe the preliminary feasibility of measuring the safety of mobilising ICU patients receiving vasoactive drugs.

**OUTCOME MEASURES** Key outcomes include: Hypothetical recruitment rate for a future randomised controlled trial; follow-up rate of participants for day-60 outcomes.

**POPULATION** Adult patients admitted to the intensive care units.

**ELIGIBILITY** For patient participants:

Inclusion criteria: Patients admitted to the ICU who are receiving vasoactive drugs; age greater than or equal to 18 years old; expected to remain admitted to the ICU for at least 24 hours post-enrolment.

Exclusion criteria: Patient expected to die imminently; mobilisation is contraindicated by the nature of patients existing injuries; where it is clear from the medical records that participants are prisoners or offenders on probation; patient and/or their consultee is unable to speak English; patients with neuromuscular disease or acute brain injury or spinal cord injury.

**DURATION** 01/11/2018 – 09/08/2019

## 1. INTRODUCTION

### 1.1 BACKGROUND

Muscle wasting in an intensive care unit (ICU) population is a considerable concern as it has been found to be fast-developing during an ICU admission (Puthucheary et al., 2013). Muscle weakness extends substantially beyond an ICU stay and is associated with deficits in physical functioning and quality of life (Fan et al., 2014). These deficits are known to be long term (Dowdy et al., 2006) having been demonstrated five years after an ICU stay (Herridge et al., 2011). These long-term complications have also been associated with increased healthcare costs (Lone et al., 2016).

Early mobilisation as part of physical rehabilitation has been recommended as a strategy to help address these poor physical outcomes and is advocated in several practice guidelines for ICUs (NICE, 2009, Girard et al., 2017). Early mobilisation is mobilisation occurring whilst the patient is still on the ICU (Bailey et al., 2007). Examples of mobilisation can include:

‘turning and moving in bed, active-assisted and active exercise, use of cycling pedals in bed, sitting over the edge of the bed, standing, stepping in place, transferring from the bed or chair, chair exercises and walking’ (Gosselink et al., 2008, p. 1190).

The evidence base for early mobilisation has developed substantially (Connolly et al., 2016), with a recent increase in the number of randomised clinical trials (Wright et al., 2018, Morris et al., 2016, Schaller et al., 2016, Moss et al., 2015, Denehy et al., 2013, Schweickert et al., 2009).

These have demonstrated beneficial effects for ICU patients such as improved ability to mobilise (Schaller et al., 2016), less delirium (Schweickert et al., 2009) and a decreased length of stay (Schaller et al., 2016). Furthermore, these benefits of improved mobility and function have continued to be measured at discharge from hospital (Schaller et al., 2016, Schweickert et al., 2009). Indeed, six months after critical illness, meta-analysis has demonstrated an increased amount of days out of hospital (Tipping et al., 2017). Early mobilisation is also regularly reported as being safe with low rates of adverse events recorded (Nydahl et al., 2017, Sricharoenchai et al., 2014, Bailey et al., 2007, Stiller et al., 2004).

### 1.2 RATIONALE FOR CURRENT STUDY

Trials of early ICU mobilisation have shown mixed results to date, with some studies concluding no evidence of beneficial effect of mobilisation on short term outcomes (Denehy et al., 2013, Morris et al., 2016, Moss et al., 2015) and limited long-term beneficial effects (Wright et al., 2018, Morris et

al., 2016, Denehy et al., 2013, Moss et al., 2015). Further, concern remains over potential adverse outcomes resulting from physical rehabilitation interventions on intensive care. Firstly this has arisen from a non-statistically significant increase in mortality demonstrated in a recent meta-analysis (Tipping et al., 2017) requiring further investigation (Cuthbertson and Goddard, 2017). Secondly there are methodological limitations in previous studies, which include a wide variety of defining adverse event criteria (Nydahl et al., 2017), a lack of recording of adverse events (Connolly et al., 2016) and concerns around the heterogeneous population in an ICU and whether safety differs for each individual (Tipping et al., 2017). Therefore measuring the relative benefits and harms of early mobilisation in different subgroups of the ICU population is a current research priority (Connolly et al., 2016, Cuthbertson and Goddard, 2017, Parry et al., 2018)

One subgroup of interest are those patients receiving vasoactive drugs, such as inotropes (drugs aiding contraction of the myocardium) and vasopressors (drugs that constrict the blood vessels to help maintain blood pressure) (Bangash et al., 2012). If a patient requires vasoactive drugs to maintain cardiovascular stability, there may be more risk of adverse events occurring during mobilisation because there is less cardiovascular reserve to cope with the demands of exercise (Stiller and Phillips, 2003). The evidence for the safety of early ICU mobilisation with patients who are receiving vasoactive drugs consists of limited observational data (Rebel et al., 2018, Boyd et al., 2018, Hickmann et al., 2016, Nievera et al., 2016). The current evidence is insufficient to accurately guide clinicians to know when it is safe to start mobilising this patient group.

Greater understanding is required, therefore there is a need for a future randomised controlled trial (RCT) answering the question 'Is it safe to mobilise ICU patients receiving vasoactive drugs? However, before a robust trial can be designed, a study is required to address several uncertainties. To address these uncertainties, it is proposed to carry out an exploratory observational study to prepare to investigate the safety of mobilising ICU patients receiving vasoactive drugs.

This protocol presents phase two of this study, which aims to clarify uncertainties such as potential recruitment and follow-up rate. Additionally, clarification is required as to when clinicians are uncertain about mobilising ICU patients receiving vasoactive drugs. Further, although there is a substantial argument for the existence of equipoise in the literature, it is not known whether clinicians and patients are personally convinced of this equipoise to the extent that randomisation of patients in a clinical trial would be acceptable. Finally, information is required to inform the choice of a suitable primary outcome measure that adequately measures the effects of mobilisation in this group.

## 2. STUDY OBJECTIVES

### **Primary objective 1**

**To describe current practice in one healthcare organisation of mobilising ICU patients receiving vasoactive drugs.**

#### Secondary objectives

1. To measure the mobilisation that occurs while patients receive vasoactive drugs in terms of the type of mobilisation and type and dosage of vasoactive drugs.
2. To describe which patients receiving vasoactive drugs are not mobilised and the reasons why.
3. To measure the adverse event rate occurring in patients mobilised on vasoactive drugs.
4. To describe how clinicians judged the risk of mobilising patients receiving vasoactive drugs.
5. To measure what standard care is in relation to mobilisation treatment milestones.
6. To measure cost of care related to ICU and hospital length of stay and mobilisation received.

### **Primary objective 2**

**To describe the preliminary feasibility of measuring the safety of mobilising ICU patients receiving vasoactive drugs.**

#### Secondary objectives

##### 2 a) Recruitment

1. To measure the number of patients who would consent in principle to be recruited into an RCT on the safety of mobilising patients receiving vasoactive drugs and to describe the reasons why patients would not consent.
2. To understand the acceptability to patients and clinicians, of randomising patients receiving vasoactive drugs to an intervention or control arm in a future RCT on the safety of mobilising patients receiving vasoactive drugs.
3. To test the feasibility of clinicians and clinician researchers taking informed consent from patients or their consultees on ICU.

2 b) Sample size

1. To measure mortality, disability, physical functioning and health related quality of life outcome measures of ICU patients to inform a future sample size calculation.

2 c) Outcomes

1. To describe the feasibility of measuring mortality, physical functioning, disability and health related quality of life outcomes to inform a future primary outcome choice.
2. To measure whether an adverse event tool captures all unsafe events that occur during or immediately after early mobilisation of adult intensive care patients receiving vasoactive drugs.
3. To describe the feasibility of an adverse event tool, during clinical practice by ICU clinicians and retrospectively by researchers.

[figure not shown]
### 3. STUDY DESIGN

This study is phase two of a two phase feasibility, where phase one (IRAS 251108) is a review of current practice (figure 1).

This study (phase two) will recruit ICU patients to measure preliminary feasibility outcomes using a survey, analysis of mobilisation treatments and assessment outcomes at day 60 post-enrolment.

- a) Firstly clinicians and patients or their consultees will be surveyed about the acceptability of recruitment and randomisation into an RCT. In addition we will measure the feasibility of collecting baseline data on pre-admission function, frailty and comorbidities.
- b) Secondly, we will analyse routine mobilisation treatments of patients receiving vasoactive drugs to describe clinician's reasons for judging whether it was safe to mobilise and the feasibility of a new adverse event tool.
- c) Finally, we will describe the feasibility of measuring outcomes at day 60 to inform the selection of a primary outcome measure.

The duration of this study will be from 01/11/2018 – 09/08/2019.

*Figure 1: Outline of feasibility study.*

ICU: Intensive Care Unit; rehab: rehabilitation; AE: adverse event; SAE: serious adverse event.

### **3.1 STUDY SETTING**

This study will be based at the intensive care units at Imperial College Healthcare NHS Trust. Follow up at day 60 will be coordinated through Imperial College Healthcare NHS Trust (e.g. for telephone questionnaires), with assessment of performance-based outcomes occurring at Imperial College Healthcare NHS Trust.

## **4. PARTICIPANT ENTRY**

Current ICU clinical records will be screened for inclusion and exclusion criteria as set out below. Any uncertainties will be clarified in discussion with other members of the clinical team.

### **4.1 PRE-REGISTRATION EVALUATIONS**

No additional screening procedures will need to be carried out before participants enter the study.

### **4.2 INCLUSION CRITERIA**

#### **4.2.1 Patient participants**

- Patients admitted to the ICU who are receiving vasoactive drugs: Patients receiving vasoactive drugs are the group of interest for the potential future RCT.
- Age greater than or equal to 18 years old.
- Expected to remain admitted to the ICU for at least 24 hours post-enrolment to allow potential for mobilisation to occur.

#### **4.2.2 Clinician participants in the survey on acceptability of randomisation**

- Clinicians who work in the intensive care unit where a patient participant has been admitted. These clinicians will be answering a survey about a recently recruited patient participant.

#### **4.2.3 Clinician participants in the survey on feasibility of adverse event tool**

- An ICU clinician at the research site.
- Has used the ICU physical rehabilitation adverse event tool as part of this research study.

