- Description of the number and type of rehabilitation adverse events and serious adverse events. Recorded to measure whether the rehabilitation AE tool is fit for purpose and able to capture all unsafe events that occur in this population of patients mobilising on vasoactive drugs.
- Description of number and type of rehabilitation adverse events recorded prospectively by the treating clinician and retrospectively by researcher case note review. This data will provide information on the usability of the tool and the most feasible way to record AE's in future research.
- Loss of information that occurs when the ICU rehabilitation AE tool is completed by clinicians and researchers will also be recorded to provide feasibility data. For clinicians this will be assessed by the number of mobilisation treatments on vasoactive drugs occurring in patients recruited into the feasibility study where the rehabilitation adverse event tool is not completed or incomplete. For researchers, this will be assessed by the number of mobilisation treatments on vasoactive drugs where the researcher was unable to complete tool using the information available in the case notes. Feasibility success is less than or equal to 10% loss of information.

Towards the end of the data collection period for patients on ICU, a short survey will be carried out of clinicians who completed the ICU rehabilitation adverse event tool. This survey will ask about the usability and feasibility of completing the AE tool in the context of clinical practice.

In addition to the above, the following data will be recorded for participants to further quantify standard care:

- Amount of time the patient received vasoactive drugs during the admission.
- Mobilisation occurring whilst patients are receiving vasoactive drugs, for example, by:
  - Number of patients who are mobilised whilst receiving vasoactive drugs.
  - Number of mobilisation treatment sessions on vasoactive drugs.
  - Number of days on vasoactive drugs where mobilisation treatment occurred.
  - Highest level of mobilisation achieved in each treatment session using the ICU Mobility Scale (IMS) (Hodgson et al., 2014a, Tipping et al., 2016).
  - Type and dose of vasoactive drugs patient received during mobilisation treatment.
- Patients receiving vasoactive drugs who are not mobilising, for example, by:
  - Number of days receiving vasoactive drugs where mobilisation is not occurring.

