## 6.3 CLINICIAN PARTICIPANTS IN THE SURVEY ON FEASIBILITY OF THE ADVERSE EVENT TOOL

We would like to recruit every clinician who has used the ICU physical rehabilitation adverse event tool as part of this research study. We are unable to accurately predict how many will use the tool because we are uncertain how often patient participants will be mobilised. However, a pragmatic estimate is that no more than 50 clinicians will use the adverse event tool. Therefore the sample size for this survey will be a maximum of up to **50** clinicians. If less clinicians use the tool, less clinicians will be recruited.

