#### **9.2.7 Clinician recruitment for survey on feasibility of adverse event tool**

Towards the end of data collection, clinicians who have used the adverse event tool will be sent a brief survey about the feasibility of its use. Clinicians will be emailed the survey, which will also contain an information sheet about the study. Consent for taking part in this survey will be implied by clinicians returning it to the clinical research team.

Initial approach will be in person, or via email with the survey will be sent from the clinical research team to the potential clinicians, i.e. from members of the clinical team who have routine access to clinician's contact details. Clinicians will be given adequate time for consideration and the right of

the clinician to refuse to participate without giving reasons will be respected. All clinician participants are free to withdraw at any time from the study without giving reasons.

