#### 9.3.1 Initial data collection

- Identifiable data will be accessed for this research study by members of the clinical care team. This includes the critical care clinical research nurse team employed by the NHS Trust.
- Participant recruitment into the study will be recorded in the case notes and clinicians will be informed so that they can complete the adverse event tool.

[REDACTED]

[REDACTED]

[REDACTED]

[REDACTED]

[REDACTED]

[REDACTED]

- All data collected for enrolled participants will be anonymised as soon as feasibly possible.

[REDACTED]

[REDACTED]

[REDACTED]

[REDACTED]

[REDACTED]

[REDACTED]

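### The adverse event tool survey is open only to clinicians who used the tool, so those due to use it who never did are not asked why, and survey-based usability is likely to look too favourable

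*Combined protocol and SAP*

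**What the plan says.** Four places in the protocol define who receives the survey on the adverse event tool.

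- Section 4.2.3 (eligibility): an ICU clinician at the site who "Has used the ICU physical rehabilitation adverse event tool as part of this research study".
- Section 5.5 (procedures): "a short survey will be carried out of clinicians who completed the ICU rehabilitation adverse event tool".
- Section 6.3 (sample size): "We would like to recruit every clinician who has used the ICU physical rehabilitation adverse event tool as part of this research study". The maximum of 50 follows from a judgement that "a pragmatic estimate is that no more than 50 clinicians will use the adverse event tool".
- Section 9.2.7 (recruitment): "clinicians who have used the adverse event tool will be sent a brief survey about the feasibility of its use".

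The group expected to use the tool is wider. Section 9.3.1 says that enrolment is noted and "clinicians will be informed so that they can complete the adverse event tool". Under Section 5.5 the tool falls due only when a mobilisation treatment is carried out.

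Non-completion is measured separately. Section 5.5 counts the mobilisation treatments on vasoactive drugs in enrolled patients "where the rehabilitation adverse event tool is not completed or incomplete", and sets a limit: "Feasibility success is less than or equal to 10% loss of information". The same section compares prospective recording by clinicians with retrospective recording by researchers, and records the time taken to complete the tool (success is under 5 minutes).

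Objective 2c.3 in Section 2 is to describe how feasible the tool is for ICU clinicians in practice and for researchers working retrospectively.

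**The concern.** The survey selects respondents on something close to the outcome it is meant to describe. If the tool is too long, unclear or poorly timed for some clinicians, one likely result is that they never use it. Those clinicians know most about what stops the tool being used, and every wording of the eligibility rule leaves them out.

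No other stated procedure recovers their reasons. The loss-of-information outcome gives a count. The protocol does collect reasons elsewhere: for declining hypothetical recruitment (5.4.1), for stopping a mobilisation treatment and for not mobilising (5.5), and for day-60 outcomes that were not completed (5.6). It lists none for a tool that was not completed.

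Two things are at stake. The survey's picture of usability is likely to be favourable compared with that of all clinicians due to use the tool. And if the 10% limit is exceeded, the team will know that forms were missed but not whether workload, form length, unclear items or lack of awareness was the cause, which is what it would need to know before a future trial.

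**Working it through.** **1. The plan's own figure.** The only number attached to the survey is the maximum of 50 (Section 6.3). It is a pragmatic ceiling on the number of *users*, with no formula, rate or precision behind it, so there is nothing to reproduce. The documents give no count of clinicians due to use the tool.

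**2. Who is in and who is out.**

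| Clinician who mobilised an enrolled patient on vasoactive drugs | Under *used* (4.2.3, 6.3, 9.2.7) | Under *completed* (5.5) |
|---|---|---|
| Completed the tool every time | In | In |
| Completed it at least once, skipped it at other times | In | In |
| Only ever left it incomplete | In | Arguably out |
| Never used it | Out | Out |

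Only the last row is clearly shut out. The third row turns on wording that differs between sections. For the second row, the survey questions are not in the protocol, so it is unknown whether skipped occasions are asked about.

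**3. How large the effect on a survey rating could be.** Let *f* be the share of clinicians due to use the tool who never did, and *p*(u) and *p*(n) the proportions of users and never-users with a favourable view. Then

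all-due proportion = (1 − *f*) × *p*(u) + *f* × *p*(n)

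excess of the users-only figure = *f* × (*p*(u) − *p*(n))

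The documents give none of these values. As an assumption, take *p*(u) = 80% and vary the others:

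| *f* | *p*(n) = 80% | *p*(n) = 40% | *p*(n) = 0% |
|---|---|---|---|
| 10% | 0.10 × 0 = 0 points | 0.10 × 40 = 4 points | 0.10 × 80 = 8 points |
| 30% | 0.30 × 0 = 0 points | 0.30 × 40 = 12 points | 0.30 × 80 = 24 points |

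When there are never-users, the excess is zero only if they hold the same view as users.

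**4. What the 10% limit does and does not bound.** Suppose the loss is exactly 10% of treatments and comes wholly from never-users, and that each user carries out *k* treatments for every one by a never-user. Then

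*f* / (*f* + (1 − *f*) × *k*) = 0.10, so *f* = 0.10*k* / (0.90 + 0.10*k*)

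- *k* = 1: 0.10 / 1.00 = 10% of clinicians
- *k* = 2: 0.20 / 1.10 = 18.2%
- *k* = 3: 0.30 / 1.20 = 25%
- *k* = 5: 0.50 / 1.40 = 35.7%

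Passing the criterion therefore limits non-use by treatment, not by clinician. Conversely, if never-users treat as often as everyone else (*k* = 1), 30% never-users means at least 30% of treatments lost, and the criterion fails.

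**The case against.** The strongest reply is that feasibility does not rest on the survey. The loss-of-information outcome does not select on use: every qualifying treatment by a never-user counts against the tool, against a stated limit. The comparison of clinician and researcher recording adds a second view. If loss is heavy, Section 5.1 already calls for further consideration. Asking users about usability is a defensible choice in an exploratory study, no success criterion is tied to the survey, and Section 8 plans description only. A usability rating from someone who never used the tool would also be hard to interpret.

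Most of this stands. It confines the point to the survey and to missing reasons, and it means that what to seek from never-users is reasons, not ratings. It does not close the gap, because a count of missed forms does not explain them.

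A reader might go further and infer three things that the documents do not support.

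- *Everyone who failed to complete the tool goes unasked.* Occasional skippers are eligible on any wording, and partial completers are eligible under three of the four.
- *Usability is overstated as a matter of fact.* That is a probable direction. The number of never-users and their views are unknown.
- *The completion-time result is biased in a way that a wider survey would cure.* Time exists only where the tool was completed, and changing who is surveyed does not alter that.

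**Conclusion.** The point holds in a limited form. The survey omits clinicians who were due to use the tool and never did, no other procedure asks for their reasons, and survey-based usability is likely to be somewhat favourable as a result. The direction assumes that never-users think less well of the tool than users do, which is plausible but not shown. The size cannot be found from the documents; the 0 to 24 points above rests wholly on assumed inputs. Overall feasibility is partly protected by the loss-of-information outcome, although that outcome bounds non-use by treatment and gives no reasons. No stated decision rule depends on the survey, so this is a worthwhile low-cost improvement rather than a necessary correction. Separately, the mismatch between *used* and *completed* needs to be reconciled.

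**What to change.** - In Sections 4.2.3, 5.5, 6.3 and 9.2.7 together, define the survey population as every clinician who carried out a mobilisation treatment in an enrolled patient receiving vasoactive drugs, and so was due to complete the tool. Basing it on patient reviews would be too wide, because a review that leads to no mobilisation gives no occasion to use the tool. This change also removes the conflict between *used* and *completed*.
- Add one question on reasons for not completing, or only partly completing, the tool.
- Report the numbers due, ever-used and responding, with users and never-users shown separately: ratings and reasons from users, reasons only from never-users.
- Restate the maximum of 50 as a number of clinicians due to use the tool. The present figure estimates users, so it cannot be assumed to cover the wider group.
- State that completion time applies to completed tools only.

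The cost is small: wording changes in four sections and one question in an emailed survey where consent is implied by return. The case-note review in Section 5.5 already covers each qualifying treatment, so the list of clinicians due can be drawn from it if the notes identify who treated. The downsides are a slightly larger survey and a possibly lower response rate among never-users, which is why the numbers due and responding should be reported.
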